10.0.1 Secondary Endpoints

Phase I:

- Time to irAE reduction by at least 1 grade from the initiation of CD24Fc treatment.

- Time to all irAEs reduced to ≤ 1 (by NCI CTCAEv5.0) from the initiation of CD24Fc treatment.
- Time to resume ICI treatment from the initiation of CD24Fc treatment.
- Recovery rate (reduction of irAE by one grade) at D42.

Patients who have not been documented to have above events will be censored at the date of the latest clinical assessment that documented as being free of events.

Phase II:

- Time to all irAEs reduced to ≤ 1 (by NCI CTCAEv5.0) from the initiation of CD24Fc treatment. Patients who have not been documented to have the event will be censored at the date of the latest clinical assessment that documented as being free of event.
- The use of steroids and other drugs (drug, dose, duration).
- Overall response rate (ORR) after retreatment with ICI with or without CD24Fc after resolution of irAE.
- Progression free survival (PFS) will be calculated as the time from initiation of ICI to first documented evidence of disease progression or death, whichever comes first. Alive patients who have not been documented to have progression will be censored at the date of the latest clinical assessment that documented as being free of progression.
- Overall survival (OS) will be calculated as the time from diagnosis to death. Alive patients will be censored at the date of the latest follow-up visit.

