	
Demographic and background characteristics obtained at enrollment will be listed and summarized. Descriptive statistics will be used to summarize changes of biomarkers from baseline in clinical laboratory parameters for this cohort, and use of steroids (drug, dose, duration) and other treatment for irAE.
 
To assess toxicity: Toxicity is evaluated by NCI CTCAEv5.0. The type, grade, frequency and proportion of toxicities noted during the treatment period will be reported, along with associated 95% confidence interval of proportion. All adverse events noted by the investigator will be tabulated according to the affected body system. In phase I lead-in study, dose limiting toxicity is defined as any new AE of \geqgrade 3 that are outside the spectrum of irAEs.
 
To assess time to recovery from irAE (time to reduction of irAE by at least one grade), time to all irAEs reduced to \leq1, and time to resume ICI treatment: The date of starting treatment (i.e., Day 1) will be used for all time events in the study. Kaplan-Meier plots and confidence intervals will be used to summarize outcomes. Medians and associated 95% confidence intervals will be calculated, and comparisons between groups will be performed by log-rank tests. Cox proportional hazard models will be used to explore association between covariates and outcomes.
 
To assess recovery rate of irAE by CD24Fc (reduction of irAE by one grade) at D42 and response rate of ICI: The fractions will be reported along with 95% two-sided confidence intervals. Comparisons between arms will be performed by Fisher's Exact tests. We will also characterize the proportion who remain that either respond or have stable disease, compared to those who progress.
 
To assess PFS and OS: Kaplan-Meier plots and confidence intervals will be used to summarize PFS, and OS; 1-year OS rate will be reported; medians and associated 95% confidence intervals will be calculated, and comparisons between groups will be performed by log-rank tests. Cox PH models will be used to explore association between outcomes and covariates.
 
As exploratory analysis, we will summarize descriptively the relationship of response rates to tumor type (lung, GI, melanoma, breast, prostate) and to cellular immune response and explore the relationship using logistic regression.

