0. OBJECTIVES

0.0 Phase I study:

0.0.0 Primary Objective:

To determine the safety and tolerability of CD24Fc in patients with advanced solid tumors who developed debilitating irAEs from immune check point inhibitors (ICIs)

0.0.1 Secondary Objectives:

- 1) time to irAE reduction by at least 1 grade
- 2) time to all irAEs reduced to grade ≤ 1
- 3) time to resume ICI treatment
- 4) recovery rate (as defined by reduction of irAE by one grade) at D42

0.1 Randomized phase II study:

0.1.0 Primary Objective:

To determine if CD24Fc shortens the recovery time of irAE and increases the recovery rate of irAE in cancer patients with G2 or 3 irAEs

0.1.1 Secondary Objectives:

- 1) To estimate the time to all irAEs reduced to ≤ 1
- 2) To record the use of steroids (drug, dose, duration) and other treatment for irAE
- 3) To record the time to resume ICI treatment
- 4) To estimate the preliminary overall response rate (ORR), progression free survival (PFS), and 1-year overall survival (OS) after treatment with or without CD24Fc
- 5) To determine if CD24Fc treatment changes the levels of inflammatory markers in the plasma

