therapy, rare but life-threatening complications have been described [13, 14]. A systematic review including 5,744 NSCLC patients from 23 studies treated with PD-1 or PD-L1 ICIs reported a global incidence of AEs of 64% (14% grade ≥ 3) with anti-PD-1 and 66% (21% grade ≥ 3) with anti-PD-L1 mAbs [15]. The incidence of grade 3 or 4 toxicity with the combination was increased compared with either single agent (59 versus 21 and 28 percent, respectively, for nivolumab and ipilimumab) in cancer patients [16, 17]. These irAEs can affect any organ (Figure 3), which including but not limited to skin, gastrointestinal tracts, lung, liver, heart, bone marrow, have unique features and require new management strategies that are distinct from those of chemotherapy and molecularly targeted therapy [18]. Of note, those patients who develop severe irAEs might benefit the most from ICIs [19, 20]. Among all irAEs captured in the largest World Health Organization (WHO) database VigiBase (N=24,079), pneumonitis and colitis are the most common observed irAEs with median time of irAE onset (IQR) of 48 (16-114) and 51 (24-105) days, respectively [21]. Little is known at this point regarding the safety and efficacy of retreatment with immunotherapy after an irAE. Much of the information available is based on retrospective studies [22-24]. In the largest observational WHO database VigiBase (N=6123), 28.8% of the initial irAE leading to the discontinuation of ICI therapy were observed again after a rechallenge with the same ICI [21]. In a rechallenge, colitis, hepatitis, and pneumonitis had higher recurrence rates compared with other irAEs. Thus, irAE represents a major hurdle in the clinical application of ICIs. For many patients this could mean delay, and potentially discontinuation, from life-prolonging treatment. Success in reducing irAE could make a transformative impact in the outcome of cancer immunotherapy, however, the mechanism of irAE related to ICIs is still not well understood, hinders the development of strategies to treat and prevent these toxicities.

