5.0 Inclusion Criteria

Patients must meet all of the following criteria to be eligible for study entry.

- 1) Ability to understand and willingness to sign an informed consent form.
- 2) At least 18 years of age.
- 3) Histologically confirmed advanced solid tumors.

- 4) Patients must have grade 2 or 3 irAEs from at least one ICI-containing regimen. Both newly emerging and persistent irAEs are allowed. Systemic steroid therapy or any other form of immunosuppressive therapy for irAEs is allowed. The specific irAEs are:
 - a. Grade 2-3 Diarrhea/Colitis: Patients with ≥ 4 stools per day or moderate-severe increase in ostomy output compared to baseline but not life-threatening diarrhea;
 - b. Grade 2-3 Pneumonitis: Mild to moderate (grade 2) or severe (grade 3) symptoms (including hypoxia, shortness of breath, requiring oxygen) but not life-threatening respiratory compromise requiring urgent intervention (e.g., tracheostomy or intubation)
 - c. Grade 2-3 Renal irAE: Creatine increased between 1.6-6.0 x ULN or ≤ 3.0 x baseline if baseline was abnormal, eGFR or creatinine clearance ≥ 15 ml/min/1.73m² but not life-threatening consequences or requiring dialysis.
 - d. Grade 2-3 Hepatic irAE: AST/ALT/ALP levels 3-20 x ULN, and T bilirubin increased ≤ 5 x ULN
 - e. Grade 2-3 Skin Rash: moderate (10-30% body surface area, BSA) to severe ($>30\%$ BSA) but not life-threatening skin lesions or Stevens-Johnson syndrome.
- 5) ECOG performance status <2 . ([Appendix 1](#)).
- 6) Life expectancy of ≥ 3 months at the time of enrollment.
- 7) All patients must have a pretreatment absolute neutrophil count (ANC) $\geq 1,000$ / μ L, hemoglobin ≥ 8 gm/dL and a pretreatment platelet count of $\geq 75,000$ / μ L obtained within 14 days prior to 1st dose of treatment.
- 8) Female subjects who are of non-reproductive potential (i.e., post-menopausal by history – no menses for ≥ 1 year; OR history of hysterectomy; OR history of bilateral tubal ligation; OR history of bilateral oophorectomy). Or, female subjects of childbearing potential must have a negative serum or urine pregnancy test within 72 hours prior to the first study drug administration.

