6.5 Concomitant Therapy

Concomitant ICI and chemotherapies are not allowed during the study period.

Patients may receive ongoing supportive and palliative care (e.g., nutritional support, pain control) as clinically indicated throughout the study. Bisphosphonate therapy is allowed as part of supportive care before or after the study. Steroids are permitted in the study as outline in section 6.2. Patients enrolled to the study will receive steroid treatment as well as other recommended treatment for a given irAE if recommended per the treating physician. Patients who develop urgent complications in previously documented sites of disease may receive palliative radiation therapy. Continuation on the protocol therapy will be determined by discussions with the sponsor and the investigator, if medically appropriate.

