10.2 Statistical Analysis

Demographic and background characteristics obtained at enrollment will be listed and summarized. Descriptive statistics will be used to summarize changes of biomarkers from baseline in clinical laboratory parameters for this cohort, and use of steroids (drug, dose, duration) and other treatment for irAE. We will adjust steroids use in analyses. Subgroup analyses will be performed separately by the status of Steroids use.

To assess toxicity: Toxicity is evaluated by NCI CTCAEv5.0. The type, grade, frequency and proportion of toxicities noted during the treatment period will be reported, along with associated 95% confidence interval of proportion. All adverse events noted by the investigator will be tabulated according to the affected body system. In phase I lead-in study, dose limiting toxicity is defined as any new AE of \geq grade 3 that are outside the spectrum of irAEs.

To assess time to recovery from irAE (time to reduction of irAE by at least one grade), time to all irAEs reduced to ≤ 1 , and time to resume ICI treatment: All time points will be started from Day 1 of CD24Fc treatment. Kaplan-Meier plots and confidence intervals will be used to summarize outcomes. Medians and associated 95% confidence intervals will be calculated, and comparisons between groups will be

performed by log-rank tests. Cox proportional hazard models will be used to explore association between covariates and outcomes.

To assess recovery rate of CD24Fc (reduction of irAE by at least one grade) at D42 and response rate of ICI: The fraction of patients who experience a PR or CR will be determined by dividing the number of responders by the total evaluable patients. The fraction will be reported along with 95% two-sided confidence intervals. Comparisons between groups will be performed by Fisher's Exact tests. We will also characterize the proportion who remain that either respond or have stable disease, compared to those who progress.

To assess PFS and OS: Kaplan-Meier plots and confidence intervals will be used to summarize PFS, and OS; 1-year OS rate will be reported; medians and associated 95% confidence intervals will be calculated, and comparisons between groups will be performed by log-rank tests. Cox PH models will be used to explore association between outcomes and covariates.

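### Phase II PFS is timed from the start of ICI rather than from randomisation, so it does not measure the stated objective of PFS after CD24Fc or placebo

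*Combined protocol and SAP*

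**What the plan says.** The Phase II secondary objective in section 0.1.1, repeated in the synopsis, is: "To estimate the preliminary overall response rate (ORR), progression free survival (PFS), and 1-year overall survival (OS) after treatment with or without CD24Fc".

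Section 10.0.1 defines PFS as "the time from initiation of ICI to first documented evidence of disease progression or death, whichever comes first". It does not say whether this is the first ICI start or a restart after the interruption. The neighbouring Phase II endpoint, time to all irAEs at grade 1 or less, is timed from the start of CD24Fc.

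The synopsis says: "The date of starting treatment (i.e., Day 1) will be used for all time events in the study". Section 10.2 has a parallel sentence: "All time points will be started from Day 1 of CD24Fc treatment". Both stand in the paragraph on irAE recovery times and time to resume ICI. PFS and OS have a separate paragraph, which gives no time origin and specifies Kaplan-Meier curves, medians, log-rank tests and Cox models. Delayed entry is not mentioned.

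Three other provisions fix where an ICI start can fall:
- Section 5.0: "Patients must have grade 2 or 3 irAEs from at least one ICI-containing regimen".
- Section 6.5: "Concomitant ICI and chemotherapies are not allowed during the study period".
- Section 6.1.1: retreatment with ICI is considered two weeks after the third dose, at the treating physician's discretion.

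**The concern.** An endpoint meant to describe what happens after randomised treatment should start its clock at randomisation or very close to it. Here neither possible ICI start does so. The first start comes before enrolment for every patient. A restart comes after randomisation and happens only in some patients.

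PFS is one of the few checks on whether CD24Fc interferes with the anti-tumour effect of ICI, which section 10.4 treats as a stopping concern. The other anti-tumour endpoints do not fill the gap: ORR is defined after ICI retreatment, and OS is timed from diagnosis (a parallel problem, not pursued here). As written, no anti-tumour endpoint is anchored at randomisation. An undefined origin also leaves a choice between two very different PFS analyses to be made after the data are seen.

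**Working it through.** **Plan's own figure.** The only Phase II power statement concerns the recovery rate: 50% versus 80%, 36 per arm, one-sided Fisher's exact test at 0.05, 81%. Exact enumeration gives 80.9%, so it reproduces. PFS has no stated sample size, event count, effect size or power, and no stated figure changes with the fix.

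**Reading 1: first ICI start.** Let L be the time from ICI start to Day 1 and T the PFS time from Day 1. The definition analyses L + T for every patient, and ordinary Kaplan-Meier counts each patient as at risk during L, when a death would have prevented enrolment.

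Inputs:
- From the documents: 36 per arm; irAE onset after ICI start (section 1.0, pneumonitis and colitis) with "median time of irAE onset (IQR) of 48 (16-114) and 51 (24-105) days"; screening of 1 to 14 days.
- Assumed: L log-normal with median 50 days and IQR 24 to 105, plus screening; exponential T; 1 year of follow-up; HR 0.5; two-sided 5% log-rank; no progression before Day 1.

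For a 90-day control median, true 6-month PFS is 0.5^(182/90) = 25%. Simulation with 2,000 to 3,000 trials per scenario gives:

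| Control median from Day 1 | Reported median from ICI start | Power, Day 1 origin | Power, ICI-start origin |
|---|---|---|---|
| 90 days | about 175 days | about 77% | about 62% |
| 150 days | about 240 days | about 68% | about 60-62% |
| 180 days | not tabulated | about 62% | about 58% |
| 365 days | not tabulated | about 45% | about 42% |

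Repeat runs differ by about 2 to 3 points. At the 90-day median, reported 6-month PFS is about 50% instead of 25%. In the direction of harm (HR 2, same median) the loss is larger, from 81% to 46%.

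With no true effect, rejection stays near 5% for both origins at medians of 90, 150, 180 and 365 days. L is fixed before randomisation and balanced between arms in expectation.

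A second simulation (6-month control median, HR 0.5, 600 runs, log-SD of L 1.0) varied the lead time. Power was 61-66% from Day 1, against 56%, 51% and 47% from ICI start for median lead times of 1.6, 3 and 6 months. Control medians rose from about 5.7-5.9 months to about 8.5, 10.5 and 14.4 months. Longer lead times matter because persistent irAEs are eligible.

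**Reading 2: ICI restart.** Suppose, as an assumption, that restart follows one-grade recovery at the plan's own rates:
- 0.50 × 36 = 18 control patients and 0.80 × 36 = 28.8, about 29, CD24Fc patients.
- Removing progression before Day 42, with a 6-month median and no PFS effect: 0.5^(42/(6 × 30.4)) = 0.85. Then 18 × 0.85 = 15 and 28.8 × 0.85 = 25 (rounded) have a PFS time.
- With no true effect, the apparent CD24Fc/control progression rate ratio is 0.86, 1.00, 1.17 or 1.25 if patients who recover only with CD24Fc have 0.67, 1, 1.5 or 2 times the hazard of the others.
- Power at HR 0.5 falls to about 38-41%.

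**The case against.** Several objections have force.

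- **Day 1 rule.** A reader might infer that the PFS definition flatly contradicts it. The synopsis wording is literally universal, but the sentence and its counterpart in section 10.2 both sit in the irAE-recovery and ICI-resumption paragraph and can be read as limited to those endpoints. The conflict is arguable. The mismatch with the objective does not depend on it.
- **Broken randomisation.** A reader might infer that the PFS comparison is biased between arms. On the first-start reading it is not; the type I error is preserved. Loss of randomisation follows only from the restart reading, which is less likely: where the protocol means a restart it speaks of resuming or of retreatment, including in the ORR entry just above PFS. The 18 versus 29 split also assumes that restart equals one-grade recovery, whereas section 6.1.1 leaves restart to discretion.
- **Size.** The larger power losses need short PFS medians. PFS is an unpowered secondary endpoint intended for preliminary estimation.
- **Pre-entry progression.** Entry guarantees survival to Day 1, not freedom from progression. If earlier progressions counted as events, median inflation would be smaller than shown.
- **Other safeguards.** Section 10.4 has a Bayesian ORR stopping rule that this definition does not touch. That rule pools both arms and so is not a randomised comparison.

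These points limit the consequences. None makes the ICI start a suitable origin for the stated objective.

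**Conclusion.** The point holds as a mismatch between the PFS definition and its objective, and should be corrected. On the natural reading the harm is inflated curves and medians (for example about 175 days reported for a true 90) and some loss of power: about 15 points at a 90-day control median, 3 to 4 points at 180 to 365 days, for HR 0.5. There is no material false-positive bias on that reading. These sizes rest on assumed PFS medians, hazard ratios, follow-up and lead-time distribution, and on no progression before Day 1; only the irAE-onset figures, the screening window and the arm size come from the documents. On the less likely restart reading the harm is more serious, because the analysed groups are selected by a post-randomisation event that treatment may influence.

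**What to change.** In section 10.0.1, define Phase II PFS as the time from randomisation to first documented progression or death in all randomised patients, whether or not ICI is restarted. Randomisation is preferable to Day 1 because a randomised patient who is never dosed has no Day 1. State the same origin in the PFS paragraph of section 10.2 and in the synopsis. Report any PFS from ICI start or restart as descriptive only, labelled as such.

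The cost is mainly wording, and reported PFS will look shorter. It is not quite free of data questions: Tables 1 and 2 schedule no tumour imaging, while section 8.1 measures response and progression against baseline and later measurements. The plan should therefore state which existing tumour assessment nearest randomisation serves as the baseline. Making the change before unblinding removes a post hoc choice of origin.

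### OS is timed from diagnosis with no delayed entry, which inflates 1-year and median OS; the PFS origin is ambiguous and the synopsis Day 1 rule may contradict both

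*Combined protocol and SAP*

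**What the plan says.** Section 10.0.1 (Phase II) defines the two survival endpoints with different origins:

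- OS: "Overall survival (OS) will be calculated as the time from diagnosis to death". Living patients are censored at their latest follow-up visit. It does not say which diagnosis is meant.
- PFS: "Progression free survival (PFS) will be calculated as the time from initiation of ICI to first documented evidence of disease progression or death". It does not say whether this is the original or the resumed ICI. The neighbouring ORR bullet is explicit: "Overall response rate (ORR) after retreatment with ICI with or without CD24Fc after resolution of irAE".

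The same section times the irAE endpoints "from the initiation of CD24Fc treatment".

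On analysis, the PFS and OS paragraph of Section 10.2 says: "Kaplan-Meier plots and confidence intervals will be used to summarize PFS, and OS; 1-year OS rate will be reported". Medians, log-rank tests and Cox models follow. That paragraph names no time origin and does not mention delayed entry.

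The synopsis (Statistical Analysis) says: "The date of starting treatment (i.e., Day 1) will be used for all time events in the study". The sentence stands in the paragraph on irAE recovery and ICI resumption. Its counterpart in 10.2, under the same heading, is "All time points will be started from Day 1 of CD24Fc treatment".

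The objective in Section 0.1.1 and the synopsis is to estimate 1-year OS after treatment with or without CD24Fc. Section 5.0 requires "Histologically confirmed advanced solid tumors" and a grade 2 or 3 irAE from at least one ICI-containing regimen.

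**The concern.** A patient must be alive to be randomised. The interval from diagnosis to randomisation is therefore survival that every trial patient is certain to have. An ordinary Kaplan-Meier curve started at diagnosis counts this interval as time at risk, although no death could have been observed in it. Anyone diagnosed 12 months or more before entry is a 1-year survivor by construction. The reported 1-year rate and median would then depend partly on how long ago patients were diagnosed, and could not be read as survival after study treatment.

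PFS has a related problem. If the origin is the original ICI, it precedes enrolment, and a progression before randomisation could count as an event. If it is the resumed ICI, PFS is undefined for patients who never resume, and the comparison is confined to a subset formed after randomisation. Two analysts following the text could report different populations.

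Section 10.4 is concerned that CD24Fc might promote tumour growth, and Section 1.5 expects the results to inform a phase III trial. OS and PFS serve both purposes.

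**Working it through.** **Figures in the documents.** There is no expected OS, no expected PFS and no diagnosis-to-entry interval, so there is no OS figure to reproduce. The only phase II power figure is 81% for Day 42 recovery (50% against 80%, 36 per arm, one-sided Fisher's exact test at 0.05). It reproduces at 80.9% and does not depend on this point.

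**Does diagnosis always precede entry?** Yes. Whether the word means first cancer diagnosis, diagnosis of advanced disease or diagnosis of the irAE, Section 5.0 requires it to have happened by entry. Only the length of the lead differs.

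**Formula.** Let L be the lead from diagnosis to entry and S(t) = 2^(-t/m) the survival from entry with median m. Randomisation and Day 1 are treated as the same time. With at least 12 months' follow-up after entry, nobody is censored before 12 months from diagnosis. Kaplan-Meier from diagnosis then estimates the average of S(max(0, 12 - L)) in place of S(12). Because S falls with time, this is larger for every L above 0.

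**Assumed inputs.** m = 12 months, so true 1-year OS is 2^(-12/12) = 50%. Leads are typically 3, 6, 12 or 24 months and take one of three shapes: constant, exponential with that mean, or lognormal with that median and log-sd 0.7 to 1.0.

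*Constant lead:*
- L = 3: 2^(-9/12) = 59.5%
- L = 6: 2^(-6/12) = 70.7%
- L = 12 or more: 100%
- Median: 12 + L, that is 15, 18, 24 or 36 months

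| Typical lead (months) | 1-year OS, constant | 1-year OS, exponential | 1-year OS, lognormal | Median OS, lognormal (months) |
|---|---|---|---|---|
| 0 (truth) | 50% | 50% | 50% | 12 |
| 3 | 59.5% | about 60% | 63-65% | 16-17 |
| 6 | 70.7% | about 70% | 75-76% | 20-22 |
| 12 | 100% | about 80% | 87-89% | 29-33 |
| 24 | 100% | about 88% | 95-97% | not run |

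The exponential and lognormal columns are simulated. The lognormal medians use 14 months' follow-up after entry. Numerical integration of the formula gives the same lognormal 1-year rates.

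**If diagnosis meant the irAE**, with an assumed lead of 0.5 to 1 month, the inflation is small: 2^(-11.5/12) = 51.5% and 2^(-11/12) = 53.0%.

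**Other survival levels.** With a lognormal lead of median 6 months, true 1-year OS of 12.5%, 35.4%, 63.0% or 70.7% (median OS 4, 8, 18 or 24 months) reads 47-50%, 66-67%, 82% or 86%.

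**Between-arm difference at 1 year**, assumed hazard ratio 0.5. The truth is 2^(-12/24) - 2^(-12/12) = 70.7% - 50% = 20.7 points.
- Constant lead of 3: 77.1% - 59.5% = 17.7 points. Constant lead of 6: 84.1% - 70.7% = 13.4 points.
- Lognormal leads of median 3, 6, 12, 24: 15-16, 11, 5-6 and 1-3 points.
- The difference does not always shrink. With a 4-month control median, the truth is 35.4% - 12.5% = 22.9 points. A constant 3-month lead gives 2^(-9/8) - 2^(-9/4) = 45.8% - 21.0% = 24.8 points. A lognormal 3-month lead gives 23.4 (log-sd 0.7) or 21.2 (log-sd 1.0).

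**Type I error.** Two-sided 5% log-rank tests from diagnosis with no treatment effect rejected in 4.5-5.8% of 8,000 simulated trials per setting. Randomisation balances the lead in expectation, so the test is not shifted toward either arm. A constant lead costs no log-rank power.

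**The case against.** **The synopsis may already cure it.** Read literally, the Day 1 sentence covers OS and PFS, matches the objective and leaves nothing inflated. But it sits under the irAE and ICI-resumption heading, as does its counterpart in 10.2, while 10.0.1 is the specific definition and names diagnosis. Read broadly, the synopsis contradicts 10.0.1; read narrowly, the defect stays. The text needs editing either way.

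**Silence is not exclusion.** Section 10.2 does not rule out delayed entry. True, but neither section provides for it, so the plan followed as written gives the ordinary estimator.

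**The size is uncertain.** This stands. Constant leads fall outside the lognormal bands, so the table shows all three shapes. The lead is undocumented; only the direction is firm.

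**The 1-year difference is not a planned test, and the hazard ratio of 0.5 is not in the documents.** This also stands. The planned comparison is the log-rank test, whose size holds. The harm lies mainly in the reported 1-year rates and medians.

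**Day 1 would serve as well as randomisation.** It would also remove nearly all the guaranteed time. Randomisation is preferable for a comparison of arms because Section 10.1 foresees a gap before first dose, and events in that gap should count.

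**PFS from randomisation may need a new baseline scan.** Section 8.1.2 already requires target lesions to be measured at baseline. The phase II calendar lists no imaging, which limits PFS under any origin.

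**Conclusion.** The concern holds. As written, 10.0.1 and 10.2 produce 1-year and median OS that are too high for the stated objective, on every reading of diagnosis. With an assumed 12-month median from entry, a true 50% reads roughly 59-65% at a 3-month lead and 80-100% at a 12-month lead, but only 51-53% if diagnosis means the irAE. These sizes rest on assumed survival and lead distributions; the upward direction does not. The synopsis and 10.0.1 must be reconciled, and the PFS origin must be made unambiguous.

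The weight is moderate. OS and PFS are preliminary, unpowered secondary endpoints. Type I error, the co-primary endpoints and the ORR monitoring in Section 10.4 are untouched. The change should be made, but it does not threaten the trial's main conclusion.

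**What to change.** - **OS (10.0.1):** define as randomisation to death from any cause, with 1-year OS read at 12 months from randomisation.
- **PFS (10.0.1):** define as randomisation to the first progression after randomisation or death, in all randomised patients.
- **Synopsis and 10.2:** state the same origin in the PFS and OS paragraphs, and limit the synopsis Day 1 sentence to the irAE and ICI-resumption endpoints.
- **Supplementary analyses:** any analysis from diagnosis or ICI start should say which diagnosis or ICI start is meant and use delayed entry at randomisation. With 72 patients the early risk sets may be very small, so this should not be the main analysis.

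The cost is a wording change that uses a date the trial already records. Table 2 and Section 6.1.1 plan survival checks for up to 1 year, anchored on the trial and not on diagnosis. Two related matters should be settled at the same time. The synopsis allots only 3 months for follow-up, data collection and analysis; if that governs, late entrants would be censored before 12 months from randomisation. The phase II calendar also lists no tumour imaging. The one drawback is that the survival figures will look less favourable.
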